8.6.4.5 Change in PRO measures

For some PRO Measures (PROMIS SexFS, PROMIS Fatigue Short Form and PGI-S), not all protocol versions mandated their collection. Subjects originally enrolled using protocol versions 2.0 were not required to collect these measures. To handle such cases, denominators used for analysis will only include the subjects mandated to collect the particular PRO.

IIEF

Descriptive summary tables will be presented for each of the 5 sexual function domain scores (Erectile function, Orgasmic function, Sexual desire, Intercourse satisfaction and Overall satisfaction) and change from baseline scores by treatment regimen and visit.

The change from baseline in each sexual function domain score to Week 24 will be analysed via MMRM in the same manner as the change from baseline in total testosterone (see Section 8.6.3.1), however 90% confidence intervals (instead of 95%) will be presented for all inferences.

The number and proportion of subjects achieving a minimal meaningful difference in the change in IIEF erectile function domain score will be summarised by treatment regimen at each visit and overall.

In addition the change from baseline in the IIEF domains will also be summarised and analysed as described above by erectile function baseline severity (No dysfunction, mild, moderate and severe), baseline total testosterone (<200ng/dL vs \geq 200ng/dL) as assessed by ICON central labs and end of treatment total testosterone (<300ng/dL, 300-500 ng/dL and >500ng/dL) as assessed by ICON central labs.

PROMIS SexFS

Descriptive summary tables will be presented for each of the 3 sexual function domains scores (Interest in Sexual Activity, Erectile Function, Satisfaction with Sex Life), 2 interfering factors raw

scores and change from baseline scores (domain and interfering factor raw scores) by treatment regimen and visit.

The change from baseline in each sexual function domain score and 2 interfering factor raw scores to Week 24 will be analysed via MMRM in the same manner as the change from baseline in IIEF domain scores including subgroup analysis by baseline total testosterone (<200ng/dL vs \geq 200ng/dL) and end of treatment total testosterone (<300ng/dL, 300-500 ng/dL and >500ng/dL) as assessed by ICON central labs.

PROMIS Fatigue Short Form

A descriptive summary table will be presented for the PROMIS Fatigue Short Form standardised T-Score and change from baseline score by treatment regimen and visit.

The change from baseline to Week 24 will be analysed via MMRM in the same manner as the change from baseline in IIEF domain scores including subgroup analysis by baseline total testosterone (<200ng/dL vs \geq 200ng/dL) and end of treatment total testosterone (<300ng/dL, 300-500 ng/dL and >500ng/dL) as assessed by ICON central labs.

BFI

A descriptive summary table will be presented for the global fatigue score and change from baseline score by treatment regimen and visit.

The change from baseline to Week 24 will be analysed via MMRM in the same manner as the change from baseline in IIEF domain scores including subgroup analysis by baseline total testosterone (<200ng/dL vs \geq 200ng/dL) and end of treatment total testosterone (<300ng/dL, 300-500 ng/dL and >500ng/dL) as assessed by ICON central labs.

SF-36

Descriptive summary tables will be presented for each of the 8 general health domain scores and 2 component scores and change from baseline scores by treatment regimen and visit.

The change from baseline in each domain and component score to Week 24 will be analysed via MMRM in the same manner as the change from baseline in IIEF domain scores including subgroup analysis by baseline total testosterone (<200ng/dL vs \geq 200ng/dL) and end of treatment total testosterone (<300ng/dL, 300-500 ng/dL and >500ng/dL) as assessed by ICON central labs.

PGI-S

Descriptive summary tables will be presented for each of the 3 status items and associated change from baseline scores by treatment regimen and visit.

The change from baseline in each status item to Week 24 will be analysed via MMRM in the same manner as the change from baseline in IIEF domain scores including subgroup analysis by baseline total testosterone (<200ng/dL vs \geq 200ng/dL) and end of treatment total testosterone (<300ng/dL, 300-500 ng/dL and >500ng/dL) as assessed by ICON central labs.

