2.1 Primary objective(s)

The primary objective is to demonstrate the efficacy of BGS649 to normalise total testosterone levels (300-1000 ng/dL [10.4-35 nmol/L]) in $\geq 75\%$ of subjects after 24 weeks of treatment.

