7.1.3 Definitions relative to efficacy criteria

7.1.3.1 Total Testosterone

Testosterone Normalisation

A subject is deemed to have achieved testosterone normalisation if their total testosterone value is between 300-1000 ng/dL (10.4-35 nmol/L) inclusive.

To allow for a potential 10-25% decrease in total testosterone that can occur due to diurnal variation in the afternoons (given current testing is restricted to mornings), a stricter secondary definition of normalisation will be used. A subject is deemed to have achieved the secondary definition of testosterone normalisation if their total testosterone value is between 350-1170 ng/dL (12.15-40.6 nmol/L) inclusive. The secondary definition boundaries were derived by averaging the testosterone value that a 25% decrease in would result in the primary definition boundary with the primary definition boundary itself.

Testosterone Overshoot

A subject is deemed to have testosterone overshoot if their total testosterone value is greater than 1000 ng/dL (35 nmol/L).

Time to first Testosterone Normalisation

Time to first Testosterone Normalisation is defined as the time (in days) from the date of first dose of study medication until the date of the first occurrence of testosterone normalisation during the treatment period.

Subjects who do not achieve testosterone normalisation will be censored at their final testosterone assessment during the treatment period (Up to Visit 8).

End of Treatment Testosterone

End of treatment testosterone is defined as the Week 24 total testosterone assessment for subjects that completed the treatment period. For subjects that discontinued the treatment period early, the last on-treatment testosterone assessment will be used as their end of treatment testosterone value.

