8.6.1 Analysis methods

For binary outcomes the proportion of subjects with a response will be summarised and compared between treatment regimens using Fisher's Exact Test.

For all continuous outcomes, where appropriate, a mixed model repeated measure model (MMRM) analysis will be performed. Analyses will include the fixed, categorical effects of treatment, visit, and treatment-by-visit interaction, as well as the continuous, fixed covariates of the associated baseline value and baseline-by-visit interaction. An unstructured covariance matrix will be used to model the within-subject errors. If the model with the unstructured covariance matrix fails to converge, other covariance structures, including Toeplitz, compound symmetry, and spatial power, will be considered. The denominator degrees of freedom will be calculated according to the Kenward-Roger method. Significance tests for treatment differences (individual BGS649 doses vs. Placebo and between BGS649 doses) will be based on least-squares means.

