8.6.3.2 Change from Baseline in Total Testosterone

A descriptive summary table will be presented for Total Testosterone values and change from baseline in Total Testosterone by treatment regimen and visit using both ICON central lab and GLP lab assessed testosterone.

Change and percentage change from baseline in Total Testosterone up to Week 24 using the ICON central lab assessed values will be analysed using an MMRM model as described in Section 8.6.1. Least squares means and standard errors will be presented for each visit, p-value and 2-sided 95% confidence interval for treatment differences (BGS649 doses vs. Placebo) will be presented for each visit. Significance tests will be based on least-squares means using a two-sided $\alpha = .05$.

A figure presenting the least square mean change from baseline in total testosterone at each visit by treatment regimen will also be provided.

Change from baseline in Total Testosterone up to Week 12 using the GLP lab assessed values will be analysed using an ANCOVA model with treatment as a fixed effect and the associated baseline value as a covariate. Least squares means and standard errors will be presented for each visit, p-value and 2-sided 95% confidence interval for treatment differences will be presented for each visit. Significance tests will be based on least-squares means using a two-sided $\alpha = .05$.

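### PRO treatment contrasts within strata of end-of-treatment testosterone (SAP 8.6.4.5) condition on a result of treatment and are not valid treatment effects

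*SAP*

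**What the plan says.** SAP 8.6.4.5 first plans an overall MMRM for each PRO score, with 90% intervals. For the IIEF it then adds that "the change from baseline in the IIEF domains will also be summarised and analysed as described above", split by baseline erectile-function severity, by baseline total testosterone, and by "end of treatment total testosterone (<300ng/dL, 300-500 ng/dL and >500ng/dL) as assessed by ICON central labs". PROMIS SexFS, PROMIS Fatigue, BFI, SF-36 and PGI-S follow the same pattern: "analysed via MMRM in the same manner as the change from baseline in IIEF domain scores including subgroup analysis by baseline total testosterone", and then also by the end-of-treatment strata.

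The model being repeated is a treatment comparison. SAP 8.6.1 says: "Significance tests for treatment differences (individual BGS649 doses vs. Placebo and between BGS649 doses) will be based on least-squares means". SAP 8.6.3.2, the total-testosterone analysis that the PROs follow, says: "p-value and 2-sided 95% confidence interval for treatment differences (BGS649 doses vs. Placebo) will be presented for each visit".

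SAP 7.1.3.1 defines the stratifier: "End of treatment testosterone is defined as the Week 24 total testosterone assessment for subjects that completed the treatment period". For men who stop early, "the last on-treatment testosterone assessment will be used as their end of treatment testosterone value". SAP 2.1 gives the aim of the trial: "The primary objective is to demonstrate the efficacy of BGS649 to normalise total testosterone levels".

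**The concern.** The list in 8.6.4.5 puts two baseline classifiers and one post-randomisation classifier under the same instruction. Baseline subgroups keep the randomised comparison intact. The end-of-treatment strata do not, because arm membership helps decide which stratum a man falls into.

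Every man entered with testosterone below 300 ng/dL on two samples (protocol 9.3.1, criterion 3). A placebo man who ends at 300-500 rose without drug; a treated man in that stratum got there on drug. They may differ in any prognostic factor tied to testosterone, and adjusting for the baseline PRO score removes only the part that score carries.

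Protocol 9.2 expects clinical benefit to come through the rise in testosterone. Comparing arms at similar testosterone therefore also removes much of the effect of interest.

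The tables would carry p-values and intervals that read as the treatment effect at a given testosterone level. A real benefit could look small, absent or reversed.

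**Working it through.** **The plan's own figure.** The SAP gives no figure for these subgroup analyses. The only relevant one is 67 per dose group with 85% power (SAP 5: 75% goal, 90% true rate, one-sided 2.5%). A normal approximation with continuity correction gives n = 66.3, so 67, with power 0.855. The exact binomial rule at n = 67 needs at least 58 responders and has power 0.871. The figure is sound and this point does not affect it; 67 is used below only as an arm size.

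**Number of contrasts, from the documents.**
- Scores: IIEF 5, SexFS 3 + 2, Fatigue 1, BFI 1, SF-36 8 + 2, PGI-S 3; total 25.
- Strata: 3. Pairs among four arms: 6, of which 3 are against placebo.
- Week 24 contrasts: 25 x 3 x 6 = 450. Against placebo: 25 x 3 x 3 = 225.

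**Assumptions for the illustration (not in the documents).** End-of-treatment testosterone is normal with mean 250-280 ng/dL on placebo and 450-550 on active drug, SD 100-150 (the same in both arms), and 67 men per arm. PRO change is scaled so that higher is better.

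**Expected cell sizes** (67 x normal tail area):

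| Arm and cell | Mean | SD 100 | SD 150 |
|---|---|---|---|
| Placebo, >500 | 250 | 0.42 | 3.20 |
| Placebo, >500 | 280 | 0.93 | 4.77 |
| Active, <300 | 450 | 4.48 | 10.63 |
| Active, <300 | 550 | 0.42 | 3.20 |

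Some cells may hold almost no one.

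**Selection bias with no drug effect on the PRO, 300-500 stratum.** Let c be the correlation of testosterone with a latent prognosis, and r that of prognosis with PRO change. Then

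bias (SD) = c x r x (mean z active - mean z placebo),

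where z is testosterone standardised within its own arm and averaged over the stratum (truncated-normal mean). Placebo men in this stratum come from the upper part of their distribution, treated men from the lower part, so the difference is negative: -0.98 (280 v 450, SD 150) to -2.21 (250 v 550, SD 100).
- c = 0: bias 0.
- c = 0.2, r = 0.3: 0.06 x -0.98 = -0.06 SD.
- c = 0.5, r = 0.5: 0.25 x -2.21 = -0.55 SD.
- After ANCOVA on a baseline PRO score correlated 0.5 with prognosis (simulation, 2,000,000 per arm): -0.05 to -0.44 SD.

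A negative c would reverse the sign.

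**Loss of a mediated benefit, no shared cause.** Suppose a 0.5 SD benefit acts wholly through testosterone. Mean testosterone differs between arms by 170-300 ng/dL overall, but by only 23-79 ng/dL within 300-500. The ratio of within-stratum to overall difference is 0.136-0.276, so the stratum shows 0.5 x 0.136 = 0.07 to 0.5 x 0.276 = 0.14 SD.

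**Second set of assumptions.** Placebo mean 240, SD 80; drug adds 160-220 ng/dL; a latent factor explains half the testosterone variance. With no drug effect and a factor-PRO correlation of 0.2-0.4, the two lower strata show -0.19 to -0.57 SD. With a mediated effect of 0.2 SD per 100 ng/dL, the randomised difference is 0.32-0.44 SD. The two lower strata then show 0.11-0.16 SD without a shared cause, and -0.08 to -0.44 SD with one.

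**The case against.** The strongest reply is that little depends on these tables. Protocol 13.5.1 treats all analyses as exploratory with no multiplicity adjustment, no decision rule uses the PROs, and the overall ITT contrast for every score is reported as well. That is correct, and it caps the seriousness. It does not make the contrasts interpretable: an exploratory label addresses status and multiplicity, not bias, and nothing in the SAP says these contrasts are non-randomised.

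The reading rests on cross-references. Section 8.6.4.5 does not itself say dose versus placebo, and it cites 8.6.3.1, whereas the MMRM text is in 8.6.3.2. The natural reading is still treatment inference. On 8.6.3.2 alone the count would be 225; the 450 follows from the all-pairwise wording of 8.1.4, 8.6.1 and 8.6.1.1. Sparse cells may leave some contrasts inestimable.

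The illustration can be challenged too. Three of the four active scenarios imply more than 90% normalisation, no placebo rate is documented, and SexFS, Fatigue and PGI-S (9 of the 25 scores) were not required under protocol version 2.0, so fewer than 67 men may contribute. The ranges above compare active drug with placebo. Between two active doses (450 v 550) the z difference is only -0.58 to -0.75, giving about -0.03 to -0.19 SD. These points limit what can be said about size; the principle does not depend on them.

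Finally, a warning label alone might suffice. It would help, but would leave up to 450 labelled p-values that do not answer the testosterone-PRO question, which SAP 8.8.4 addresses without treatment contrasts.

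**Conclusion.** The concern holds. As written, SAP 8.6.4.5 gives treatment inference within strata of a post-randomisation form of the primary efficacy variable, and those contrasts are not valid treatment effects. That conclusion follows from the definitions in the SAP and needs no numerical assumption.

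The size and sign of the bias do rest on assumptions. Selection bias is zero if testosterone and the PRO share no cause; attenuation of a testosterone-mediated benefit remains even then.

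The harm is misreading of supportive PRO tables. The plan should be changed, but nothing in the confirmatory result depends on it.

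**What to change.** In SAP 8.6.4.5, for every PRO, remove the least-squares treatment differences, p-values and confidence intervals by end-of-treatment testosterone. Show those strata descriptively only, with a note that arms within a stratum are not randomised comparisons. Keep the overall ITT contrasts and the subgroups by baseline testosterone and baseline erectile-function severity. Correct the cross-reference from 8.6.3.1 to 8.6.3.2.

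Examine the testosterone-PRO link through SAP 8.8.4 (scatter plots) and the models in 8.8.4.1 and 8.8.4.2, labelled as non-causal association. If a model is wanted for the remaining PROs, extend the 8.8.4.1 model to them.

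The cost is SAP wording and fewer inferential tables; no new data are needed. Some exploratory within-stratum inference is lost. The two models in 8.8.4 cover only 4 of the 25 scores (three SexFS domains and IIEF erectile function), so without an extension most PROs keep only scatter plots. Section 8.8.4 also uses the PP population whereas 8.6.4 uses ITT, so the population for any extended model should be stated.

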8.6.4.6 Change in physical activity, sleeping pattern and strength

Physical Activity

Descriptive summary tables will be presented for the average number of minutes spent per day over the 7 days within each activity category, total daily steps, total daily activity counts and maximum daily activity counts by treatment regimen and visit. The change from baseline in the average number of minutes spent within each activity category, total daily steps and total activity counts to Week 24 will be analysed via MMRM in the same manner as the change from baseline in total testosterone (see Section 8.6.3.1).

Sleeping Pattern

Descriptive summary tables will be presented for each sleeping pattern parameter (The average length of awakenings [minutes], number of awakenings, number of minutes asleep [minutes], number of minutes awake [minutes] and proportion of time spent asleep during the sleep period) and associated change from baseline by treatment regimen and visit. The change from baseline in each parameter to Week 24 will be analysed via MMRM in the same manner as the change from baseline in total testosterone (see Section 8.6.3.1).

Grip Strength

A descriptive summary table will be presented for the average grip strength and associated change from baseline by treatment regimen and visit. The change from baseline in average grip strength to Week 24 will be analysed via MMRM in the same manner as the change from baseline in total testosterone (see Section 8.6.3.1).

A subgroup analysis of the change from baseline in grip strength by baseline total testosterone (<200ng/dL vs ≥200ng/dL) as assessed by ICON central labs will be conducted. Descriptive summaries and analysis up to Week 24 as described above will be presented.

8.6.4.7 Change in Semen Parameters

Descriptive summary tables will be presented for each semen parameter (semen volume, sperm count, concentration, motility percentage, total motile count and morphology percentage) and change from baseline scores by treatment regimen and visit.

The change from baseline in each semen parameter to Week 20 will be analysed via MMRM in the same manner as the change from baseline in total testosterone (see Section 8.6.3.1).

A subgroup analysis of the change from baseline in semen parameters by baseline assessment timing (prior to first dose of study medication vs after first dose of study medication) will be conducted. Descriptive summaries and analysis up to Week 20 as described above will be presented.

A shift table of change from baseline in sperm concentration categories to post baseline categories will be generated by treatment regimen and visit.

The number and proportion of subjects moving from azoospermia at baseline to oligospermia post baseline and oligospermia at baseline to normal post baseline will be summarised by treatment regimen at each visit and overall.

8.6.4.8 Change in Bioavailable testosterone and Free testosterone

Descriptive summary tables will be presented for bioavailable and free testosterone values and change from baseline values by treatment regimen and visit.

The change from baseline in bioavailable and free testosterone up to Week 24 will be analysed via MMRM in the same manner as the change from baseline in IIEF domain scores.

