13.5.4 Analysis of Exploratory Endpoints

The analysis of exploratory endpoints will be performed on the ITT population.

Data will be summarised by treatment regimen and visit.

For each continuous parameter, change from Baseline will be assessed with a MMRM analysis, with treatment regimen as a factor and the Baseline value as a covariate. The adjusted mean difference between treatments will be presented along with a 95% CI for the time-points of interest.

For binary outcomes the proportion of subjects with a response will be summarised and compared between treatment regimens using Fisher's Exact Test.

A more detailed description will be presented in the SAP.

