8.1.4 Statistical significance

Unless otherwise stated, all statistical testing will be two-sided and conducted at the significance (alpha) level of 0.05. Two-sided 95% confidence intervals (CIs) will be provided when relevant. All four treatment regimens will be assessed by pairwise comparisons, and no adjustment for

multiplicity will be made.

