8.6.3.4 Change in LH and FSH

Descriptive summary tables will be presented for LH and FSH values and change from baseline in LH and FSH by treatment regimen and visit.

The change from baseline in LH and FSH up to Week 24 will be analysed via MMRM in the same manner as the change from baseline in total testosterone (see Section 8.6.3.1).

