8.6.4.1 Change in oestradiol, inhibins (A and B) levels, DHT and testosterone/oestradiol ratio

Descriptive summary tables will be presented for oestradiol, inhibin A, inhibin B, DHT, testosterone/oestradiol ratio and DHT/testosterone ratio values, change from baseline values and

percentage change from baseline values by treatment regimen and visit. High sensitivity Oestradiol values will be summarised together with the Oestradiol values assessed by the Central lab.

The change and percentage change from baseline in each parameter up to Week 24 will be analysed via MMRM in the same manner as the change from baseline in total testosterone (see Section 8.6.3.1). Additionally a figure of absolute oestradiol will be provided by treatment regimen.

In addition the number and proportion of subjects with oestradiol values < 11 pg/mL will be summarised by treatment regimen at each visit.

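### SAP 8.6.4.8 borrows the IIEF method, so bioavailable and free testosterone get 90% intervals while total testosterone and the other modelled hormones get 95%

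*SAP*

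**What the plan says.** SAP 8.6.4.8 gives bioavailable and free testosterone an MMRM of change from baseline up to Week 24, to be run "in the same manner as the change from baseline in IIEF domain scores". It says nothing of its own about the confidence level.

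The IIEF paragraph of SAP 8.6.4.5 takes over the total testosterone model and then departs from it: "however 90% confidence intervals (instead of 95%) will be presented for all inferences".

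For total testosterone itself, SAP 8.6.3.2 states that "p-value and 2-sided 95% confidence interval for treatment differences (BGS649 doses vs. Placebo) will be presented for each visit", and on testing, "Significance tests will be based on least-squares means using a two-sided" alpha of 0.05. SAP 8.6.3.4 handles the gonadotrophins the same way: "FSH up to Week 24 will be analysed via MMRM in the same manner as the change from baseline in total testosterone". SAP 8.6.4.1 does so for oestradiol, inhibins A and B, DHT and the two ratios: "analysed via MMRM in the same manner as the change from baseline in total testosterone".

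The SAP default in 8.1.4 is "Two-sided 95% confidence intervals (CIs) will be provided when relevant". For continuous exploratory endpoints, Protocol 13.5.4 says: "The adjusted mean difference between treatments will be presented along with a 95% CI for the time-points of interest". Protocol 13.5.1 also sets 95% as its general default. SAP Section 9 lists only the vitamin D cut-off as a change from the protocol.

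**The concern.** Bioavailable testosterone is calculated, with total testosterone and SHBG as the measured quantities (Protocol 11.3.1), and it is scheduled at the same treatment-period visits as total testosterone. Readers of the report will set the total, bioavailable and free results beside each other. If the level changes between the tables, the two fractions will seem to separate from placebo more readily for a reason that has nothing to do with the data.

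The reference also looks misplaced. Body composition, cardiometabolic markers, bone markers, activity, sleep, grip strength and semen parameters are all sent to the total testosterone model. Apart from these two hormone measures, only the patient-reported outcomes use the IIEF method. No reason is given for putting two laboratory measures on the questionnaire rule.

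**Working it through.** **Following the references**

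| Measure | SAP section | Method it points to | Interval level |
|---|---|---|---|
| Total testosterone | 8.6.3.2 | own MMRM | 95% |
| LH, FSH | 8.6.3.4 | total testosterone | 95% |
| Oestradiol, inhibins A and B, DHT, ratios | 8.6.4.1 | total testosterone | 95% |
| IIEF domains | 8.6.4.5 | total testosterone, level changed | 90% |
| Bioavailable and free testosterone | 8.6.4.8 | IIEF domains | 90% |

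No other section restores 95% for the last row. The table covers every hormone with a planned post-baseline model. SHBG is only summarised at baseline (8.4.2), and cortisol, TSH, FT4 and prolactin are only listed (8.7.2.2).

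The SAP cites Section 8.6.3.1 for the total testosterone model, but that section holds the secondary normalisation definition. The model is in 8.6.3.2. The wording still identifies the intended model, so the chain is not broken.

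**Interval width**

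The half-width is a multiplier times the standard error, and the standard error does not depend on the level.

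- 90%: multiplier 1.645
- 95%: multiplier 1.960
- Ratio: 1.645 / 1.960 = 0.839, so the 90% interval is about 16% narrower
- Inverse: 1.960 / 1.645 = 1.19, so restoring 95% widens it by about 19%

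The model uses Kenward-Roger degrees of freedom, which the documents cannot fix in advance. With t quantiles the ratio is 0.833 at 40 df, 0.837 at 100 df and 0.838 at 260 df. The result does not depend on this choice.

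**Chance of excluding zero under no effect**

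This is 1 − 0.90 = 10% per interval, against 1 − 0.95 = 5%.

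**How many intervals**

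There are 2 parameters, 3 doses against placebo and 7 post-baseline treatment visits (Day 8 and Weeks 4, 8, 12, 16, 20 and 24): 2 × 3 × 7 = 42. If no dose had any effect, the expected number excluding zero would be 42 × 0.10 = 4.2 instead of 42 × 0.05 = 2.1. The expectation holds whatever the correlation between visits. The count assumes that free testosterone is available at every visit where bioavailable testosterone is scheduled. The schedule lists bioavailable testosterone and SHBG but does not name free testosterone.

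**Agreement with the test**

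The test level in SAP 8.1.4 and 8.6.3.2 is two-sided 0.05. A contrast with p between 0.05 and 0.10 would be non-significant beside a 90% interval that excludes zero.

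**The case against.** The strongest reply is that little turns on this. The primary criterion is a proportion for total testosterone, Protocol 13.5.1 treats all analyses as exploratory without multiplicity adjustment, and no success rule or arm decision uses these intervals. That is right, and it is why the point is minor.

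Several narrower objections also carry weight:

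- **Scale.** The baseline cut-offs in SAP 8.4.2 (200 ng/dL total, 130 ng/dL bioavailable, 47 pg/mL free) show that the three measures have different scales, so raw widths cannot be compared as precision at any level. What readers do compare is whether each interval excludes zero, and that does change with the level.
- **Recoverability.** The model also reports standard errors and p-values, so a 95% interval can be reconstructed. This limits the harm but leaves the printed tables inconsistent.
- **Test level.** The IIEF wording changes the intervals presented and states no new alpha. The 10% is therefore a property of the intervals, and the rate of significant tests stays at 5%.
- **Permitted exception.** Both general defaults allow exceptions, and free testosterone is not a listed protocol endpoint. The direct conflict with Protocol 13.5.4 is therefore for bioavailable testosterone, exploratory endpoint 11. It is still undeclared in Section 9.
- **Subgroups.** The IIEF method also has subgroup analyses by testosterone level. Other questionnaire paragraphs import them explicitly and 8.6.4.8 does not, so it is unclear whether they carry over. The interval level carries over on either reading.
- **Intent.** The documents do not show whether 90% was chosen or slipped in. Either way the text needs a change: a corrected reference or a stated reason.

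None of these breaks the chain from 8.6.4.8 to 90%.

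**Conclusion.** The point holds. As written, SAP 8.6.4.8 produces 90% intervals for bioavailable and free testosterone, while every other hormone with a planned post-baseline model has 95%. For bioavailable testosterone this departs from Protocol 13.5.4 without explanation or declaration.

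The intervals are about 16% narrower, each has twice the chance of excluding zero under no effect, and up to 42 dose-versus-placebo intervals are affected. The width result needs no trial data. The count rests on free testosterone being available at all seven visits. The primary endpoint and its conclusion are unaffected, so this is a desirable correction for consistency and not a threat to the trial.

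**What to change.** In SAP 8.6.4.8, replace the reference to the IIEF domain scores with a reference to the total testosterone MMRM, citing Section 8.6.3.2 and two-sided 95% intervals. Cite 8.6.3.2 and not 8.6.3.1, which the SAP uses elsewhere for this model. State in the same sentence that no subgroup analyses by testosterone level are planned for these two measures, or name those that are.

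If the sponsor did intend 90%, give the reason in 8.6.4.8 and list the departure from Protocol 13.5.4 in Section 9. The 90% level for the patient-reported outcomes is stated openly in 8.6.4.5 but is also absent from Section 9, and this correction does not touch it. It can be listed at the same time if it is kept.

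The cost is one cross-reference and the matching confidence level in the programmed tables. No new data, model or sample size is needed.
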